6. PROCEDURES AND ASSESSMENTS

Clinical, Demographic and Laboratory Data

It has been verified that the requested data is normally acquired in the routine care of these types of patients at the referral centers for the primary investigators. Laboratory data will be obtained from routine blood draws as clinically indicated. Peak VO2 and echocardiographic parameters will be measured once during the baseline period and once at the one-year visit as clinically indicated. In those centers selected for MedaMACS, as in most centers with high volume advanced heart disease evaluation, peak VO2 and echocardiographic assessment are routine components of regular and serial evaluation. Medications, cardiac imaging, and exercise testing will occur at the discretion of the physicians caring for each study participant. Patient therapies and testing will conform to standards of care and published clinical guidelines for heart failure management.^{18, 19} Subjects will have additional functional assessment of both endurance (6 minute walk) and frailty (gait speed) one month after consent to measure early stability. Registry data will be obtained by chart review from both the electronic medical record and paper charts. Note all dates for baseline data will be by intervals rather than calendar dates. There will be a total of six data collection time points, four with face to face clinical encounters and another two by telephone: (Figure 5).

- Baseline A at consent (face to face encounter)
- Baseline B 3-6 weeks after consent (face to face encounter)
- 6 month telephone call by study site personnel
- 12 month follow-up 10-14 months after consent (face to face encounter)
- 18 month telephone call by study site personnel
- 24 month follow-up 22-26 months after consent (face to face encounter; study close)

Patient Survey

The patient survey instrument patient will assess quality of life, health-related stress, along with impression of and thresholds for consideration of VAD therapy. All survey responses are for research only and as such will be kept confidential and not be shared with members of the medical team. This written survey will be administered at Baseline A, Baseline B, the 12 month visit and again at the 24 month study close-out visit. Patients will receive the Kansas City Cardiomyopathy Questionnaire to determine disease specific quality of life and with the Euroqol-5D questionnaire including the thermometer. There will also be a brief instrument on health-related stress identical to

the tool being used in INTERMACS. The quality of life instruments will be completed independently by the patients in a single session.

After quality of life instruments have been completed, study coordinators will read a description of a VAD and provide a simple picture. The description of a VAD will include information on implantation, anticipated benefits and potential risks. The surveys will only be administered at face-to-face visits to allow a study nurse to assist with the VAD portion of the instrument. Patients will complete the VAD portion of the survey after receiving this standard information and a study nurse will be present to answer any queries about the VAD items. Similar VAD survey items were administered in the screening pilot with excellent response rates.¹⁷ Any patient who fails to complete a survey will have a missing data form filled outlining why the self-reported instruments were not completed. In all, there are 40 questions for the patients to answer in a written format, which should take approximately 35-40 minutes for most subjects. Original copies of the written survey instruments will be kept on site by study investigators and the data will be entered electronically by the coordinators or their data assistants on site (Appendix A).

Follow-up Telephone Contact at 6 and 18 Months

A telephone call will be made by local site investigators or their study staff to patients at 6 and 18 months after study enrollment, but can be replaced by face-to-face visits if occurring as part of their routine care. The major purpose of this telephone call is to assess patient vital status and important interval events such as transplantation, placement of VAD, or other major procedures. The second purpose is to estimate the number of hospitalizations after study enrollment and the frequency of other major adverse events as recalled by patients. Any major endpoint or adverse event will be confirmed or amended by review of the interim medical record by site investigators. At the time of each study follow-up visit, the records will be reviewed for evidence of any major events leading to hospitalization that might have been missed in the intervening phone interviews.

Patients will be asked the questions determining functional class and profile. They will be asked a small subset of questions from the baseline questionnaire related to preferences for resuscitation and for VAD. They will be asked to bring their medications to the telephone to list them with doses.

Clinical Assessment at 12 months

It is anticipated that patients will be seen at some time between 10 and 14 months after the baseline study. Clinical information including routine laboratory values, physical examination, and symptoms will be reported. An echocardiogram and peak oxygen consumption will be recorded if obtained for clinical indications, as is routine practice for patients with this severity of illness followed at major centers. The six minute walk functional test will be repeated along with 5 meter gait speed to assess frailty. Patients will be re-administered the questionnaires regarding functional status, quality of life, and preferences for VAD as at baseline.

End of study at 24 months

A final face to face encounter at 24 months (between 22-26 months) will be completed and the study will end at that point. Routine clinical assessment components and other study data elements will be recorded as available from the clinical record, including results of imaging and exercise testing for measurement of peak oxygen consumption, if performed at or after the 18 month time point. The six minute walk functional test will be repeated along with 5 meter gait speed to assess frailty. Patients will be re-administered the questionnaires regarding functional status, quality of life, and preferences for VAD as at baseline. Finally, at 24 months each patient

will receive the VAD survey and questionnaire to assess quality of life and perception of VAD technology. After the two year face to face visit, study participation will end.

Data Elements

A full list of data elements to be collected along with collection times may be found in Appendix B. All data will be recorded in a web based data entry system.

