For groups within which survival is > 60% at 1 year on medical therapy, a composite of survival and function will be the most important for comparison to VAD therapy. We hypothesize that it will be possible to identify a composite endpoint of survival and function that will show a 30% difference between outcomes on medical therapy and outcome with initial VAD. The nature of these survival-function endpoints will be explored during the first year of MEDAMACS data. The two simplest will be done with the endpoints of days alive out of hospital, and quality-adjusted life years according to the Euroqol. However, more complex endpoints will be tested for survival and functional scores at specific intervals. (Figure 5)

Information will be collected regarding the major adverse events that lead to hospitalization both with and without mechanical circulatory support, as listed in the data appendix: neurologic event, non-CNS bleeding, sepsis, ventricular tachyarrhythmia or ICD firing. The hospitalizations, adverse events and deaths will be attributed on site by the investigators in drop-down menus. There will be no independent adjudication of causes of hospitalizations or deaths. The general categories of causality are broad and not the focus of the primary hypotheses. Thus, the lack of formal adjudication should not compromise the data for the endpoints of death, transplant, and VAD, which are objectively determined. The secondary endpoints that relate to functional capacity and to quality of life will also be specifically determined.

Statistical Methods

Baseline data between different patient groups will be compared using student's t-test for normally distributed continuous variables and Wilcoxon Rank Sum for non-normally continuous variables. Kaplan-Meier curves will be constructed for time to death, VAD or transplant for the two-year study period. Event rates including cause-specific hospitalizations will be generated for different groups of patients and analyzed. Analysis plans for specific research questions will be developed under guidance of the DCC after approval by the Research and Publication Committee.

All summary statistics and subsequent analysis will be performed using SAS statistical software (Cary, NC).

Publications

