9. Many life-sustaining therapies are available near the end of the life. These include dialysis, breathing machines, tubes for feeing, and whether or not you would wish to be resuscitated if your breathing or heart stops beating. Has your physician talked about your wishes regarding such life-sustaining therapies?

A. Yes

B. No

C. Don't know

10. At this time, if there are any life-sustaining therapies you do not want, please circle them below:

- A. Chest compressions
- B. Being placed on a breathing machine
- C. Kidney dialysis
- D. Transfer to the Intensive Care Unit (ICU)
- E. Feeding tube if unable to eat

Part IV: Missing Data Form

Check one response regarding WHY "self-report instruments" were not completed by the PATIENT:

- _____ too sick
- _____ too tired
- _____ too stressed, anxious, and / or depressed
- _____can't concentrate
- _____ no time / too busy
- _____ too much trouble / don't want to be bothered / not interested
- _____ unwilling to complete instruments, no reason given
- _____ unable to read English and / or illiterate
- _____ administrative (check specific reason below)
 - _____No time, coordinator too busy to administer self-report instruments
 - ____Coordinator forgot to administer self-report instruments
 - _____Unable to contact patient face-to-face or per telephone
 - Patient did not return mailed self-report instruments within the
 - window for instrument completion
 - _____ other reason

(describe)_____

Part V: Supplemental Questions:

1. In general, how comfortable would you be if your life depended on interacting with technology every day? Please draw an "X" on the line below that best describes how you feel.

Highly Uncomfortable

Very Comfortable

2. Treatments for heart disease can range from pills to pacemakers and even major heart surgeries. Some patients are willing to undergo more aggressive treatment to survive, while others are reluctant to consider more aggressive therapies and wish to focus on comfort alone. Based on how you feel today, please draw an "X" on the line below to indicate how you feel about medical treatments for your heart failure.

Focus on Comfort Only

Do Anything to Survive

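### Section 6 allows all surveys only face to face, in conflict with the Missing Data Form and the Appendix B EuroQoL schedule, and leaves survivors not seen at 12 or 24 months without a quality-of-life score at that time point

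*Combined protocol and SAP*

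**What the plan says.** **Section 6, Patient Survey.** The instruments are the Kansas City questionnaire, the EuroQol with thermometer, a short health-stress instrument and the VAD survey. On timing: "This written survey will be administered at Baseline A, Baseline B, the 12 month visit and again at the 24 month study close-out visit". On mode: "The surveys will only be administered at face-to-face visits to allow a study nurse to assist with the VAD portion of the instrument". On the quality-of-life part: "The quality of life instruments will be completed independently by the patients in a single session". The VAD description is read only after that part is finished. On non-completion: "Any patient who fails to complete a survey will have a missing data form filled outlining why the self-reported instruments were not completed".

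**Section 6, visit list and telephone contact.** The 12- and 24-month visits are face to face, with windows of 10-14 and 22-26 months. The 6- and 18-month contacts are telephone calls, which a routine visit may replace. The listed call content is vital status, events, functional class and profile, medications and some preference items: "They will be asked a small subset of questions from the baseline questionnaire related to preferences for resuscitation and for VAD". The EuroQol is not listed.

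**Appendix A, Part IV (Missing Data Form).** Reasons for non-completion include "Patient did not return mailed self-report instruments within the" completion window, and "Unable to contact patient face-to-face or per telephone". Being too sick is also a listed reason.

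**Appendix B, QOL/PREFERENCES.** EuroQoL, its thermometer and its five domains are marked at all six time points. The Kansas City questionnaire, the VAD survey and the missing data survey are marked only at Baseline A, Baseline B, 12 and 24 months.

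**Use of the scores.** Aim 2.3 concerns change in quality of life. Section 8 names "quality-adjusted life years according to the Euroqol" as one of the two simplest survival-function endpoints. Section 8 gives no method for missing scores.

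**The concern.** The protocol gives sites inconsistent instructions on mode. Read literally, Section 6 forbids mailing a questionnaire and collecting the EuroQol by telephone, while one appendix has a code for a mailed questionnaire that was not returned and the other expects a EuroQol at a telephone contact. Sites could resolve this differently, and no field in Appendix B records the mode used.

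The rule is also wider than its reason. Help from a nurse with the VAD items is a good argument for supervising those items. It does not apply to instruments that patients complete unaided.

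What is at stake is the set of survivors who contribute a score at 12 and 24 months. Section 6 offers no fallback for a living patient who is not seen in the window; only the reason is recorded. If patients are missed because they are sicker, and the analysis uses whoever has a score, the medical-therapy cohort may look better on patient-reported measures, and on composites that use them, than it is. A score not collected in its window cannot be recovered later.

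**Working it through.** **1. Mode, place by place.**

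| Place | What it implies |
|---|---|
| Section 6, Patient Survey | All surveys face to face only |
| Appendix A, Part IV, mail code | Instruments may be mailed |
| Appendix A, Part IV, contact code | Telephone is a route of contact; completion by telephone is not stated |
| Appendix B | EuroQoL due at 6 and 18 months |
| Section 6, telephone contact | Those contacts are calls unless a routine visit replaces them; EuroQoL not in the listed content; some VAD-preference items are asked |

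The first row cannot stand with the second. It also cannot stand with the fourth whenever the 6- or 18-month contact is a call. The last row shows that some VAD-preference items are themselves asked by telephone.

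**2. Who is left without a score.** Under Section 6, a survivor not seen in months 10-14 or 22-26 has no Kansas City and no EuroQol score at that time point. If Appendix B is followed, EuroQoL values may exist at 6 and 18 months, but there is no Kansas City score at those contacts.

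**3. Scale of the cohort.** The plan has no figure for missed visits or missing scores. Its only size figure is 350, for about ±5% around 35% one-year mortality. With a two-sided 95% level (assumed), n = 1.96² × 0.35 × 0.65 / 0.05² = 349.6, so 350 is reproduced. At 35% mortality, 350 × 0.65 = 227.5, about 228, are alive at one year, before removing patients who received a VAD or transplant.

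**4. Bias in a mean score.** Let m be the fraction of survivors unscored, and d the mean of scored minus unscored survivors. The available-case mean exceeds the mean of all survivors by m × d. Neither m nor d is in the documents; the values below are assumptions.

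| m | Unscored of 227.5 | d = 0 | d = 10 points | d = 20 points |
|---|---|---|---|---|
| 10% | 23 | 0 | 1 | 2 |
| 20% | 46 | 0 | 2 | 4 |
| 30% | 68 | 0 | 3 | 6 |

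On the EuroQol index, an assumed gap of 0.1 to 0.3 with m of 10-30% gives 0.01 to 0.09.

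**5. Bias in change from baseline (Aim 2.3).** Here d is replaced by the gap in change, which is the gap at follow-up minus the gap at baseline. With m = 20% and a 15-point gap at follow-up, the bias is 0.20 × 15 = 3 points if the groups were equal at baseline. It is 0.20 × (15 − 15) = 0 if the same 15-point gap was already there.

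**The case against.** The strongest defence is that one supervised mode is a reasonable choice in a study that Section 8 describes as descriptive and correlative, and that mixing modes brings a mode effect. The windows are four months wide, and Section 6 reports excellent response to similar VAD items in the pilot. The mail code may be an unused entry on the form, since Appendix B schedules the form only at face-to-face time points. This makes heavy loss less likely, but it does not remove the conflict in the text or supply a rule for the patient who is not seen. Section 4 also says that telephone outcome measures are being field-tested in the pilot at 6 and 12 months, so remote collection is not foreign to the programme.

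Several stronger readings are tempting, and the documents do not support them:

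- *Medical outcomes will look better than they are.* This needs unscored survivors to be worse off and an available-case analysis. The form lists illness, but also lack of time, lack of interest, inability to read English and coordinator error. The direction is plausible, not established.
- *The form provides for completion by telephone.* It names telephone only as a way of contacting the patient.
- *Such survivors have no quality-of-life data at all.* Under Appendix B they could have EuroQoL at 6 and 18 months.
- *More than half the cohort is at risk of missing visits.* From Figure 3, 0.50 × 90 + 0.54 × 39 + 0.92 × 11 = 76 of 140 pilot patients (54%) were in Profiles 4-5. A profile is a symptom level, and those patients were enrolled; it says nothing about missed visits.
- *The contrast with VAD shrinks.* That also depends on how INTERMACS collects its scores, which is not stated.

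The six-minute walk also needs attendance, so a remote questionnaire would not complete a composite that uses the walk.

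**Conclusion.** The inconsistency over mode is certain and can be read directly from Section 6, Appendix A and Appendix B. It is also certain that Section 6, as written, leaves a survivor not seen at 12 or 24 months without a Kansas City or EuroQol score at that time point.

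Bias is possible, not shown. Its size is unknown because the documents give neither a missed-visit rate nor a score gap. The 1-6 Kansas City points rest wholly on the assumed 10-30% unscored and 10-20 point gap, apply to a mean score and assume an available-case analysis. For change from baseline the bias could be smaller, or zero. It reaches patient-reported outcomes and composites built on them. Death, VAD and transplant are followed by telephone and record review and are not affected, and days alive out of hospital does not use the surveys.

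The change is worth making because it is cheap and must be in place before the follow-up windows pass.

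**What to change.** 1. In Section 6, limit the face-to-face rule to the VAD survey (Appendix A, Part III), and name the short set of preference items asked at the 6- and 18-month calls as an exception.
2. If the 12- or 24-month visit is missed, collect the Kansas City questionnaire, the EuroQol and the stress and satisfaction items by mail or telephone within the same window.
3. Add one field to Appendix B for the mode of completion.
4. Use the Missing Data Form only when both the visit and the remote route fail, and align its reason codes with the permitted modes.
5. Reconcile Section 6 with Appendix B on EuroQoL at 6 and 18 months: either add it to the listed call content or remove it from the schedule.
6. In Section 8, state that quality-of-life results will be checked by mode.

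The cost is protocol wording, one data field, and a mailing or call only for patients who miss a visit. The downside is a possible small mode effect, which the mode field allows to be examined.

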2. SPECIFIC AIMS

Aim 1: To identify prospectively a population of ambulatory patients followed on optimal medical therapy for whom chronic heart failure limits both function and survival to a range where elective implantation of left ventricular assist devices should offer meaningful benefit. *Hypothesis: It will be possible to define baseline characteristics that predict a one year mortality of* \geq 35±5% for patients on medical therapy and \leq 25±5% in patients who have had VAD.

- 1.1 Characterize ambulatory patients with advanced heart failure by baseline variables and interval change, including functional capacity, frailty, and interest in technical intervention. There will be two baseline measurements one month a part (used to predict early stability) and a repeated set at 1 year (used to predict outcome between 1 and 2 years). These outcomes will include: a). All clinical parameters required for current risk score models and prediction, b). Follow-up values and changes from baseline to 1 month and baseline to 1 year as additional variables from which to predict outcomes on medical therapy, c). Functional capacity, quality of life, and patient preferences at baseline and after time.
- 1.2 Distinguish between risk factors that predict mortality whether therapy is medical or mechanical, and those risk factors that predict outcomes with different impact depending on whether therapy is medical or VAD. This will be stratified by whether patient is eligible for transplant or not.
- 1.3 Record outcomes for ambulatory patients with advanced heart failure for comparison to VAD, to include a). Hospitalizations, VAD, transplant, survival without VAD or transplant, b). Major adverse events leading to hospitalization, including infection, neurologic or bleeding, c). Functional capacity and quality of life, d). Eligibility for transplant, e). Changes in resuscitation status and enrollment in hospice.

Aim 2: To design an integrated endpoint of survival and objective functional assessment that provides more discrimination between chronic ambulatory heart failure and current device outcomes than survival alone.

Hypothesis: It will be possible to identify a composite endpoint of survival and function that will show a 30% difference between outcomes on medical therapy and outcome with initial VAD.

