Alanine aminotransferase/SGPT B-type natriuretic peptide (BNP) NT-pro-BNP Metabolism Total cholesterol Low density lipoprotein High density lipoprotein Triglycerides Uric acid C-reactive protein Pre-albumin Albumin Hematologic White blood cell % lymphocytes	x x x x x x x x x x x x x x x x x			X X X X X X X X X X X X X		X X X X X X X X X X X X X
Alanine aminotransferase/SGPT B-type natriuretic peptide (BNP) NT-pro-BNP Metabolism Total cholesterol Low density lipoprotein High density lipoprotein Triglycerides Uric acid C-reactive protein Pre-albumin Albumin Hematologic White blood cell % lymphocytes Hemoglobin	x x x x x x x x x x x x x x x x x x x			X X X X X X X X X X X X X		X X X X X X X X X X X X X
Alanine aminotransferase/SGPT B-type natriuretic peptide (BNP) NT-pro-BNP Metabolism Total cholesterol Low density lipoprotein High density lipoprotein Triglycerides Uric acid C-reactive protein Pre-albumin Albumin Hematologic White blood cell % lymphocytes Hemoglobin Hematocrit	X X X X X X X X X X X X X X X X X X X			X X X X X X X X X X X X X X X		X X X X X X X X X X X X X X X
Alanine aminotransferase/SGPT B-type natriuretic peptide (BNP) NT-pro-BNP Metabolism Total cholesterol Low density lipoprotein High density lipoprotein Triglycerides Uric acid C-reactive protein Pre-albumin Albumin Hematologic White blood cell % lymphocytes Hemoglobin	x x x x x x x x x x x x x x x x x x x			X X X X X X X X X X X X X		X X X X X X X X X X X X X

QOL/PREFERENCES	Baseline A	Baseline B	6m	12m	18m	24m
EuroQoL	х	x	x	x	х	х
Thermometer	х	х	х	х	х	х
5 functional domains	х	х	х	х	х	х
Kansas City Cardiomyopathy	v	V		v		V
Questionnaire	X	X		X		X
Patient VAD survey instrument	X	X		X		X
Missing data survey	X Baseline	X Baseline		X		X
EVENTS/OUTCOMES	Α	В	6m	12m	18m	24m
Death		Х	Х	Х	х	Х
Primary cause of death (assigned by PI)		Х	Х	Х	х	Х
Sudden death		Х	х	х	х	х
Transplant		Х	Х	Х	х	Х
Listed for Transplant		Х	Х	Х	х	Х
Listing status		Х	х	х	х	х
VAD, if yes then		х	х	х	х	х
Type of circulatory support		Х	Х	Х	х	Х
Device name		Х	х	х	х	х
Intended Support Strategy Other Cardiac Procedure/Surgery		x		х		x
(name)		Х		Х		Х
Chronic inotrope infusion		Х		Х		Х
Resuscitation (Code) Status		Х		Х		Х
Hospice		Х		Х		Х
Recovery of EF to ≥40%		Х		Х		Х
Current NYHA Functional Class		Х		Х		х
Current INTERMACS Profile		Х		Х		Х
Hospitalization, reason for admission		Х		Х		Х
Heart failure with iv diuresis or inotrope		Х		Х		Х
Neurologic event		Х		Х		Х
Major bleeding (non CNS)		Х		Х		х
Transfusion		Х		Х		Х

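### Section 6 gives hospitalizations, adverse events and procedures to the 6- and 18-month calls, but Appendix B schedules almost none of them then, so capture may be incomplete in patients who die before the next visit

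*Combined protocol and SAP*

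**What the plan says.** Section 6, Follow-up Telephone Contact at 6 and 18 Months, gives the calls two purposes. The main one is to "assess patient vital status and important interval events such as transplantation, placement of VAD, or other major procedures". The second is to "estimate the number of hospitalizations after study enrollment and the frequency of other major adverse events as recalled by patients". Two record checks follow. Reported endpoints and adverse events are confirmed or corrected from the interim medical record. A wider search for events that the calls missed is also planned: "At the time of each study follow-up visit, the records will be reviewed for evidence of any major events leading to hospitalization".

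Section 6, Data Elements, states: "A full list of data elements to be collected along with collection times may be found in Appendix B". In the Events/Outcomes block of Appendix B, death, the row "Primary cause of death (assigned by PI", transplant, listing and VAD are marked at Baseline B, 6, 12, 18 and 24 months. The row "Hospitalization, reason for admission", the reason rows beneath it, the other-cardiac-procedure row, "Chronic inotrope infusion" and hospice are marked at Baseline B, 12 and 24 months only.

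These items feed planned outcomes. Aim 1.3 lists hospitalizations, major adverse events leading to hospitalization, and "Changes in resuscitation status and enrollment in hospice". Section 8 plans cause-specific hospitalization rates and names days alive out of hospital as one of its two simplest survival-function endpoints.

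**The concern.** For hospitalizations, nearly all adverse events and other procedures, the text and the schedule disagree on what is recorded at 6 and 18 months. A site that works from Appendix B has a place to enter a death at those contacts, but none for the admissions that came before it. A survivor's admissions in the same months are entered at the 12-month visit.

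Whether an event is captured could therefore depend on whether the patient survives to the next visit. If so, hospitalization and adverse-event rates on medical therapy would be too low. Days alive out of hospital would be too high, because unrecorded hospital days count as days at home. These are the figures the registry means to set beside VAD outcomes.

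**Working it through.** **The plan's own figure.** Section 8 gives about 350 patients for a precision of about ±5 points at 35% mortality. With 95% confidence (assumed, since the level is not stated), n = 1.96² × 0.35 × 0.65 / 0.05² = 349.6, so 350. The figure reproduces, and this point does not depend on it.

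**Text against schedule.**

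| Item | Purpose of the calls (Section 6)? | Marked at 6 and 18 months (Appendix B)? |
|---|---|---|
| Vital status, transplant, VAD | Yes | Yes |
| Functional class, INTERMACS profile, medications | Yes | Yes (Clinical and therapies blocks) |
| Hospitalizations and reasons | Yes | No |
| Other major adverse events | Yes | No, except ICD shock dates (therapies block) |
| Other major procedures | Yes | No |
| Chronic inotrope infusion, hospice | Not named | No |

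The first five marked outcome rows follow one pattern and the rest follow another, consistently over many rows, so damage in text extraction is an unlikely explanation. For inotropes and hospice there is a gap in the schedule but no contradiction.

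**Scale, for illustration only.** Inputs:
- One-year mortality of 35%, the hypothesised figure in Sections 2 and 8.
- Constant hazard, and no removal by VAD or transplant (assumptions).
- Decedents admitted at r = 2 or 3 times the survivor rate, which is set to 1 (assumption).
- Baseline B at month 1, and no recovery from charts (assumptions).

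Steps, per patient enrolled:
1. Hazard h = −ln(0.65) = 0.431 per year. S(1 month) = 0.965 and S(6 months) = 0.806.
2. First-year patient-time = 0.35 / 0.431 = 0.812 years: survivors 0.650, decedents 0.162.
3. Deaths in months 1-6 = 0.965 − 0.806 = 0.159, or about 55 of 350.
4. Their time after month 1 = (S(1) − S(6))/h − (5/12) × S(6) = 0.368 − 0.336 = 0.032 years, which is 3.9% of patient-time.
5. True events = 0.650 + r × 0.162, giving 0.975 (r = 2) or 1.137 (r = 3). Unrecorded events = r × 0.032, giving 0.064 or 0.096.
6. Time counted without events: understatement = 0.064/0.975 = 6.6%, or 0.096/1.137 = 8.4%.
7. Time excluded: 1 − (1 − 0.066)/(1 − 0.039) = 2.7%, or 1 − (1 − 0.084)/(1 − 0.039) = 4.7%.

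At 20% mortality the same steps give about 4-5% and 2-3%.

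**Upper case.** Suppose the 12-month event rows are also left blank for deaths in months 6-12. The affected time is then 0.315/0.431 − (11/12) × 0.65 = 0.135 years, or 16.6% of patient-time. The understatement becomes 2 × 0.135/0.975 = 28% to 3 × 0.135/1.137 = 36% with that time counted, or 13-23% with it excluded.

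**The case against.** The strongest reply is that nothing in the documents says these events are dropped. Section 6 has reported endpoints and adverse events checked against the interim medical record, and that sentence is not tied to a visit. Section 6 also names chart review as the registry's general data source. This stands, and it rules out a reading that a reader might otherwise reach, that the events are lost. It does not close the gap. The first check works on events already reported, and recall is not available from a patient who has died. The search for unreported events is the one tied to a visit. No sentence directs a site to complete these rows at death.

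Second, the 12- and 24-month columns carry death together with every event row, so a death in months 6-12 can be entered in a column that has the needed fields. This stands. It is why the main illustration is limited to deaths in months 1-6. A reader might instead treat all first-year decedent time, 0.162/0.812 = 20%, as lost. That gives 17-29% (1 − 1/1.20 to 1 − 1/1.40) with decedents excluded, or 33-43% (1 − 0.80/1.20 to 1 − 0.80/1.40) with their time counted without events. The documents do not support those figures. They include time before Baseline B, which has the rows, and they assume the 12-month column is never completed for a patient who has died.

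Third, a blank cell in this block need not mean that nothing is collected. Functional class and INTERMACS profile are blank there at 6 and 18 months but marked in the Clinical block. The analogy is fair, yet hospitalizations have no such second entry at 6 and 18 months. ICD shock dates do, so it would be wrong to say that no adverse event is scheduled then.

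Fourth, 35% is a hypothesis about a risk group that baseline characteristics might define; it is not the expected mortality of the whole cohort. That is accepted, and 35% serves only to show scale. A reader might also suppose that hospice suffers most because entry falls close to death, but the documents give no timing for it.

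**Conclusion.** The point holds as an inconsistency with a risk of bias. Section 6 and Appendix B conflict on hospitalizations, almost all adverse events and other procedures at 6 and 18 months. Inotropes and hospice share the schedule gap without being call purposes. In patients who die before the next visit these items are at risk of incomplete, differential capture, most clearly when the death is recorded at 6 or 18 months.

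Under the stated assumptions the first-year hospitalization rate would be understated by about 7-8%, or 3-5% if the affected time is excluded. It would be more if the 12-month rows are also left blank for later deaths, and less to the extent that sites recover events from charts. The admission ratio of 2-3 is an assumption without support in the documents, so only the direction and rough order of size should be relied on. Capture of death, transplant and VAD is not affected. The change should be made because the exposed items are named outcomes and practice could otherwise differ among the 12 centers.

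**What to change.** In Appendix B, mark the hospitalization row with all its reason rows, the other-cardiac-procedure row, the chronic inotrope row and the hospice row at 6 and 18 months.

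In Section 6, add a rule: when death, VAD or transplant is reported, the site completes the Events/Outcomes rows by chart review, covering the time from the last completed form to the date of the event.

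The cost is extra fields on two existing contact forms and one chart review per terminal event, with a small amount of added coordinator time. No extra visit is needed, and record review by sites is already part of the plan.
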